7.6.2 Rationale for the sample size

In the non-Japanese phase II clinical study (CR845-CLIN2101), the change from baseline in NRS score at Week 8 (mean \pm standard deviation) was -3.9 ± 2.48 , -2.8 ± 2.24 , and -3.4 ± 2.34 in the MR13A9 0.5 μ g/kg, 1.0 μ g/kg, and combined (CR845 all doses) groups, respectively, versus -1.9 ± 2.29 in the placebo group. The difference in the change from

baseline in NRS score (least squares mean \pm standard error) in each of the MR13A9 0.5 μ g/kg, 1.0 μ g/kg, and combined groups versus the placebo group was -1.8 ± 0.50 , -0.8 ± 0.52 , and -1.3 ± 0.41 , respectively.

For the present study, the MR13A9 0.5 and 1.0 μ g/kg groups were assumed to have a similar change in NRS score at Week 8 of the treatment period to that observed in the MR13A9 combined group in the non-Japanese phase II clinical study. The MR13A9 0.25 μ g/kg group, for which no efficacy results were obtained, was assumed to have about half the change in NRS score assumed above. The mean difference in NRS score between each of the MR13A9 0.25, 0.5, and 1.0 μ g/kg groups and the placebo group was assumed to be -0.6, -1.3, and -1.3, respectively, with a common standard deviation of 2.5. When the dose-response relationship for the MR13A9 0.25, 0.5, and 1.0 μ g/kg groups was evaluated using the contrast patterns shown in "13.5.2.1.1 Primary analysis," with a two-sided significance level of 5% and a sample size of 60 subjects per group, a contrast pattern of 3, 1, -2, -2 (placebo, 0.25, 0.5, 1.0 μ g/kg) produced a statistical power of 91.7%. Statistical power is more than 80% when the MR13A9 0.5 or 1.0 μ g/kg group (60 subjects per groups) was compared with the placebo group.

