With respect to the mean difference in NRS score at Week 2 of the treatment period, the MR13A9 0.5 and 1.0 μ g/kg groups were assumed to show a difference considered clinically meaningful versus the placebo group, and the MR13A9 0.25 μ g/kg group was assumed to show about half the difference above. The mean difference in NRS score versus the placebo group was assumed to be -0.4, -0.8, and -0.8 in the MR13A9 0.25, 0.5, and 1.0 μ g/kg groups, respectively, with a common standard deviation of 1.9. As with the evaluation of the doseresponse relationship at Week 8 of the treatment period, when the dose-response relationship for the MR13A9 0.25, 0.5, and 1.0 μ g/kg groups was evaluated using the contrast patterns, with a two-sided significance level of 5% and a sample size of 60 subjects per group, a contrast pattern of 3, 1, -2, -2 (placebo, 0.25, 0.5, 1.0 μ g/kg) produced a statistical power of 76.4%.

8. Subject Instructions and Management

The principal investigator or subinvestigator should sufficiently explain the significance and objectives of the study to subjects, and instruct and manage them especially for the following:

- 1) Confirm the absence of somnolence, dizziness, or similar symptoms after receiving the study drug and return home. Report any symptoms to the principal investigator or subinvestigator. Pay attention during hazardous machine operation and automobile driving during the treatment period. Avoid hazardous machine operation and automobile driving on the day of study treatment.
- 2) Maintain the symptom diary in subject every day. Record symptoms in the designated form and bring it at visit dates if any electronic diary system trouble makes the maintenance of the symptom diary impossible.
- 3) Take all prescribed drugs other than the study drug properly as instructed.
- 4) Be sure to visit the study site as scheduled. Inform the study site in advance if it is impossible to visit for some unavoidable reason. Visit the study site at the same time at every visit whenever possible.
- 5) Report the drug(s) used currently to the principal investigator or subinvestigator before participation in the study. Consult the principal investigator or subinvestigator before use about any new drug prescribed at other medical departments or hospitals or any over-the-

counter drug to be started. Report to the principal investigator or subinvestigator immediately if it was inevitable to use any drug without consultation.

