13.5 Efficacy

The FAS will be used as the primary analysis set. As a supplementary analysis, the PPS will be used for the primary analysis of the primary variable to determine the robustness of the analysis results.

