13.5.2.1 Analysis of the primary variable

13.5.2.1.1 Primary analysis

The primary analysis will be performed using a mixed-effects model for repeated measures (MMRM) with change from baseline in the mean NRS score at each time point as an objective variable; treatment group, time point, and treatment group-by-time point interaction as fixed effects; baseline mean NRS score and dynamic allocation factors, presence of prior treatment with nalfurafine hydrochloride, and presence of specific signs or symptoms to be confirmed in the screening period, as covariates; and subject as a random effect.

The analysis will include all available data obtained at each time point between Week 1 and Week 8 of the treatment period. Estimation will be performed using a restricted maximum likelihood method. An unstructured covariance structure will be used to estimate error variance. If the unstructured covariance structure fails to provide convergence, the structure that minimizes Akaike's Information Criterion (AIC), among the Toeplitz, first-order autoregressive, and compound symmetry structures, will be used. The degree of freedom will be adjusted with the Kenward-Roger method.

For the primary variable and the change from baseline in the mean NRS score at Week 2 of the treatment period, contrasts will be used to determine the dose-response relationship for the placebo group and the MR13A9 0.25, 0.5 and 1.0 μ g/kg groups. Contrast patterns (placebo, 0.25, 0.5, 1.0 μ g/kg) to be used will include (3, 1, -1, -3), (2, 2, -1, -3), (1, 1, 1, -1, -1), (3, -1, -1, -1), and (3, 1, -2, -2).

The adjusted mean change at each time point for each group and its two-sided 95% confidence interval will be presented. The adjusted mean between-difference in the change at each time point for the placebo group and the MR13A9 0.25, 0.5, and 1.0 μ g/kg groups and its two-sided 95% confidence interval as well as the p value will be presented.

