All statistical tests will be performed using a two-sided significance level of 5%; however, a two-sided significance level of 15% will be used for the analysis of between-group imbalance. Summary statistics will be presented as the number of subjects, mean, standard deviation, minimum, median, maximum, and quartile. Unless otherwise specified, data will be tabulated by group and by time point. Week 0 will be the baseline.

SAS System Release 9.4 for Windows (SAS Institute Inc.) will be used to conduct the analysis.

4. Analysis Sets

The analysis sets are defined as follows. When the full analysis set (FAS) and the per protocol set (PPS) are used as analysis sets, analyses will be performed based on the treatment group to which each subject has been allocated. When the safety set (SS) and the pharmacokinetic analysis set (PKS) are used as analysis sets, analyses will be performed based on the treatment group in which each subject has been actually treated.

- FAS: Population of subjects, excluding the following subjects: subjects with GCP violations, untreated subjects, discontinued subjects before entry to the treatment period, some of the ineligible subjects, and subjects with no available mean NRS score at baseline (Week 0)
- PPS: Population of subjects, excluding the following subjects from the FAS: ineligible subjects, discontinued subjects, deviators, and subjects with broken emergency key codes, as the subjects to be excluded from the PPS

Statistical Analysis Plan	Protocol No. MR13A9-4
	Version: 1.0

- SS: Population of subjects, excluding the following subjects: subjects with GCP violations, untreated subjects, and discontinued subjects before entry to the treatment period
- PKS: Population of subjects, excluding the following subjects from the SS: subjects with no available plasma drug concentration data

Correspondence of the analysis items and the analysis sets is shown in Table 4-1.

Table 4-1 Analysis Items and Analysis Sets

Endpoints	Analysis items	Analysis sets
Demographic and other baseline	Subject demographics	FAS, PPS, SS, PKS
characteristics	Other	SS
Treatment compliance	All items	FAS, SS
Efficacy	Primary variable (primary analysis)	FAS (primary analysis set), PPS
	Other	FAS
Pharmacokinetics	All items	PKS
Safety	All items	SS

5. Analysis Groups

- MR13A9 0.25 μg/kg group: Subjects allocated to or treated with MR13A9 0.25 μg/kg
- MR13A9 0.5 μg/kg group: Subjects allocated to or treated with MR13A9 0.5 μg/kg

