10.1.1.1 Analysis of the primary variable

10.1.1.1.1 Primary analysis

The primary analysis will be performed using a mixed-effects model for repeated measures (MMRM) with the change from baseline in the mean NRS score at each time point as an objective variable; treatment group, time point, and treatment group-by-time point interaction as fixed effects; baseline mean NRS score and dynamic allocation factors, including the presence of prior treatment with nalfurafine hydrochloride, and the presence of specific signs or symptoms to be confirmed in the screening period, as covariates; and subject as a random effect.

The analysis will include all available data obtained at each time point between Week 1 and Week 8 of the treatment period. Estimation will be performed using a restricted maximum likelihood method. An unstructured covariance structure will be used to estimate error variance. If the unstructured covariance structure fails to provide convergence, the structure that minimizes Akaike's Information Criterion (AIC), among the Toeplitz, first-order autoregressive, and compound symmetry structures will be used. The degree of freedom will be adjusted with the Kenward-Roger method.

For the primary variable and the change from baseline in the mean NRS score at Week 2 of the treatment period, contrasts will be used to determine the dose-response relationship for the placebo group and the MR13A9 0.25, 0.5, and 1.0 μ g/kg groups. Contrast patterns (placebo, 0.25, 0.5, 1.0 μ g/kg) to be used will include (3, 1, -1, -3), (2, 2, -1, -3), (1, 1, 1, -1, -1), (3, -1, -1, -1), and (3, 1, -2, -2).

The number of subjects, adjusted mean of the change, standard error, and two-sided 95% confidence interval in each group at each time point will be presented, and the adjusted mean and standard error will be presented in graphs. The adjusted mean between-group difference in the change at each time point for the placebo group and the MR13A9 0.25, 0.5, and $1.0~\mu g/kg$ groups and its two-sided 95% confidence interval as well as the p-value will be

Protocol No. MR13A9-4
Version: 1.0

presented. P-values will be presented for each contrast pattern used to examine the dose-response relationship.

Assessment time points: Weeks 1, 2, 3, 4, 5, 6, 7, and 8

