10.1.1.1.2 Sensitivity analysis

The sensitivity analyses shown below will be performed to determine the robustness of the analysis results. In the individual sensitivity analyses, as with the primary analysis, contrasts will be used to determine dose-response relationships and estimate treatment effects. However, this is not presented in graphs.

Multiple imputation (MI) will be performed 100 times.

1) MI - MMRM

Multiple imputed data will be generated in the MI procedures shown below. Each imputation data will be analyzed using the same MMRM model as that for the primary analysis, and the results of the analyses will be combined. Imputation will be performed for all available data obtained at each time point between Week 0 and Week 8 of the treatment period.

- (1) Non-monotone missing data will be imputed with a Markov Chain Monte Carlo (MCMC) method.
- (2) Monotone missing data will be imputed with an imputation formula generated using a regression model developed based on the data from all the groups.

2) Placebo MI - MMRM

Multiple imputed data will be generated in the MI procedures shown below. Each imputation data will be analyzed using the same MMRM model as that for the primary analysis, and the results of the analyses will be combined. Imputation will be performed for all available data obtained at each time point between Week 0 and Week 8 of the treatment period.

- (1) Non-monotone missing data will be imputed with an MCMC method.
- (2) Monotone missing data will be imputed with an imputation formula generated using a regression model developed based on the data from the placebo group.

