10.1.2 Other assessment variables

10.1.2.1 Change from baseline in the mean NRS score

Summary statistics will be presented. A one-sample t-test will be used for comparisons within each group. A two-sample t-test will be used for comparisons between the placebo group and each of the MR13A9 0.25, 0.5, and $1.0 \mu g/kg$ groups.

Assessment time points: Weeks 1, 2, 3, 4, 5, 6, 7, and 8, Follow-up Weeks 1 and 2

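### Conditional, low severity: if the unstructured MMRM does not converge, every fallback covariance on the list uses one variance for Weeks 1 to 8, although the power figures use SD 1.9 at Week 2 and 2.5 at Week 8

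*SAP*

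**What the plan says.** SAP 10.1.1.1.1 fits change from baseline at Weeks 1 to 8 with an unstructured error covariance, a random subject effect, REML and Kenward-Roger degrees of freedom. If that model does not converge, the structure with the smallest AIC "among the Toeplitz, first-order autoregressive, and compound symmetry structures will be used". Protocol 13.5.2.1.1 has the same list: "among the Toeplitz, first-order autoregressive, and compound symmetry structures, will be used". Neither document names a version with week-specific variances or a robust standard error.

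The dose-response contrasts at Week 8 (primary) and Week 2 come from this one model. Protocol 7.6.2 powers the Week 8 contrast "with a common standard deviation of 2.5" and the Week 2 contrast "with a common standard deviation of 1.9". Common here means common to the four groups; the two weeks have different values.

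Three planned analyses bear on the point:
- Multiple imputation, SAP 10.1.1.1.2: "Each imputation data will be analyzed using the same MMRM model as that for the primary analysis".
- Per-protocol set, Protocol 13.5: "the PPS will be used for the primary analysis of the primary variable to determine the robustness". SAP Table 4-1 agrees, listing "FAS (primary analysis set), PPS" for the primary variable.
- Week-by-week tests, SAP 10.1.2.1: "A two-sample t-test will be used for comparisons between the placebo group" and each dose group.

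**The concern.** Toeplitz, AR(1) and compound symmetry, named without a heterogeneous qualifier, each put a single variance on the diagonal. The random subject effect adds only a constant. AIC cannot select week-specific variances when no candidate has them. Kenward-Roger works within the fitted structure and does not repair a wrong one.

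If the true SD is larger at Week 8 than on average over the eight weeks, a one-variance fit understates the standard error at the primary time point. Confidence intervals would then be too narrow and contrast p-values too small. The reverse would happen at weeks with a smaller SD, such as Week 2 on the planning figures.

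**Working it through.** **Inputs.** From Protocol 7.6.2: 60 per group, two-sided 5%; differences from placebo −0.6, −1.3, −1.3 with SD 2.5 (Week 8) and −0.4, −0.8, −0.8 with SD 1.9 (Week 2). From Protocol 1.3.2.2: the observed SDs in step 3. SDs for the other six weeks are not in the documents, so every path below is an assumption.

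**1. Reproduce the plan's power.** For contrast (3, 1, −2, −2), Σc² = 18. The noncentrality is |Σcμ| / (SD·√(18/60)), with a noncentral t on 236 df.
- Week 8: 4.6 / (2.5 × 0.548) = 3.36, power 91.7%. Stated: 91.7%.
- Week 2: 2.8 / (1.9 × 0.548) = 2.69, power 76.4%. Stated: 76.4%.

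So the plan's figures rest on two variances, in the ratio 6.25 / 3.61 = 1.73.

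**2. Effect of a one-variance fit.** With complete data, equal groups and a separate mean per group and week, compound symmetry estimates the average of the eight weekly variances; AR(1) and Toeplitz come close to it. Let r = (root mean square of the weekly SDs) / (Week 8 SD). The reported Week 8 standard error is r times the true one, and the true alpha is 2[1 − Φ(1.96 r)].

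**3. Observed SDs.** Pooled by arm, using the denominators given for adverse drug reactions as arm sizes:
- CR845-CLIN2101, NRS at Week 8: √(900.26/170) = 2.30.
- MR13A9-3, VAS over two weeks: √(47,620/100) = 21.8 mm.
- CR845-CLIN2005 Part B, VAS at Week 2: √(36,023/63) = 23.9 mm.

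Dividing VAS by 10 (an assumption) and joining Week 2 to Week 8 by a straight line extended back to Week 1:
- 2.18 to 2.30: mean-square SD 2.230, r = 0.970, alpha 5.7%.
- 2.39 to 2.30: mean-square SD 2.353, r = 1.023, alpha 4.5%.

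**4. Paths through the planning SDs (1.9 at Week 2, 2.5 at Week 8).**

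| Assumed path | Mean-square SD | r | Alpha |
|---|---|---|---|
| Linear, 1.8 at Week 1 to 2.5 at Week 8 | √(37.40/8) = 2.162 | 0.865 | 9.0% |
| 1.9 until Week 7, then 2.5 | √(31.52/8) = 1.985 | 0.794 | 12.0% |
| 1.9 in Weeks 1–2, then 2.5 | √(44.72/8) = 2.364 | 0.946 | 6.4% |
| 2.5 except at Week 2 | √(47.36/8) = 2.433 | 0.973 | 5.6% |
| 1.9 in Weeks 1–2, 2.7 in Weeks 3–7, 2.5 at Week 8 | √(49.92/8) = 2.498 | 0.999 | 5.0% |

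Fitting all three structures by expected likelihood under four assumed correlation patterns gives, for the first four rows in turn, 8.9–9.0%, 9.7–12.0%, 6.4–7.2% and 5.3–5.7%. The range over paths that never exceed 2.5 is therefore about 5.3 to 12.0%. In the last row AR(1) or Toeplitz gives 5.0–6.3%, depending on the assumed correlation.

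**5. Linear path in trial units.** The pairwise 95% interval has half-width 1.96 × 2.162 × √(2/60) = 0.77 instead of 1.96 × 2.5 × √(2/60) = 0.89, and covers about 91%. At Week 2 the standard error is 2.162 / 1.9 = 1.14 times too large: alpha is about 2.6%, and power falls from 76.4% to about 67%.

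**6. Simulation checks.**
- Linear path, complete data, 1,500 runs: alpha 8.9% (Toeplitz), 8.7% (AR(1)), 8.0% (compound symmetry). With an assumed 15% dropout, 600 runs: 8.2–9.8%.
- REML fits with 15% dropout, linear path: Toeplitz standard error ratio 0.858 and alpha 9.3%; heterogeneous Toeplitz 0.997 and 5.1%.
- Same set-up, constant SD 2.3: Toeplitz 5.1%, heterogeneous Toeplitz 5.3%.
- The unstructured fit converged in 100 of 100 simulated data sets at 60 per group with 15% dropout. The data were idealised and the software was not the SAP's.

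**The case against.** The main analysis is already right: unstructured covariance has week-specific variances. The issue lies in a contingency branch with an objective, pre-specified rule, and 36 parameters with 240 subjects should seldom cause trouble. This stands. The documents give no way to compute the probability of fallback.

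The evidence for a growing SD is thin. Protocol 7.6.2 gives no source for 1.9, and 2.5 is above every Week 8 arm SD in CR845-CLIN2101 (2.18 to 2.48), so it may simply be cautious. Both are unadjusted, while the model's residual SD is conditional on baseline NRS and the allocation factors. This also stands. It is why the observed-SD figures come first, although they compare different studies and scales.

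A reader might infer that, with fallback, the planning SDs alone make the Week 8 standard error too small, or that the primary test runs at about 9%. The documents support neither. They give SDs for two of eight weeks, and the last table row meets both planning SDs with alpha at 5.0%. The 9% needs the fallback and an assumed path as well.

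There are partial checks. The Week 8 t-tests use that week's own variance but do not test the contrasts. The imputation and per-protocol reruns do test them and may converge unstructured, but they inherit the same fallback list. None replaces the primary result.

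**Conclusion.** The structural point is firm: on non-convergence the plan allows only one-variance structures, while its own power calculation uses two different variances, and neither AIC nor Kenward-Roger can make up the difference.

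The consequence is conditional. The Week 8 standard error is too small only if all three of these hold:
1. The fallback is used.
2. The residual SD after covariate adjustment grows as the unadjusted planning SDs do.
3. The SDs in the other weeks are on average (in mean square) below the Week 8 SD.

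Given fallback, alpha is about 4.5 to 5.7% on the observed SDs, about 9% on the assumed linear path, about 5.3 to 12% on assumed paths that never exceed 2.5, and can be about 5.0% if the SD exceeds 2.5 in mid-study. This is a low-severity matter, worth changing because the change is cheap.

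**What to change.** In SAP 10.1.1.1.1 and Protocol 13.5.2.1.1, put a first fallback step ahead of the present list: heterogeneous Toeplitz, heterogeneous AR(1) and heterogeneous compound symmetry, chosen by AIC. Keep the present three structures only as a last resort if none of those converges, with a robust (sandwich) standard error in that case. Deleting them outright would leave no rule if the heterogeneous models also failed. The text should also say which degrees of freedom go with the robust standard error, since Kenward-Roger is built on the model-based covariance.

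The cost is one line of text and seven more variance parameters in the fallback model: 9 for heterogeneous AR(1) or compound symmetry and 15 for heterogeneous Toeplitz, against 36 unstructured. If the SDs are in fact constant, the change in alpha is negligible (simulated 5.3% against 5.1%).

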1.3.2.2 Efficacy and safety

In a Japanese phase II clinical study (MR13A9-3), 105 previously treated hemodialysis patients with pruritus received intravenous doses of MR13A9 0.25, 0.5, 1.0, or 1.5 µg/kg, or placebo 3 times weekly for 2 weeks. With respect to efficacy, the primary endpoint of change in VAS (i.e., change based on the larger VAS value either in the morning or the evening during the 7 days, the latter half of the treatment period) (mean \pm standard deviation) was 23.4 ± 20.0 mm, 28.0 ± 18.2 mm, 32.8 ± 25.4 mm, and 41.2 ± 22.8 mm in the 0.25, 0.5, 1.0, and 1.5 μ g/kg groups, respectively, versus 26.4 \pm 22.3 mm in the placebo group. These results suggested a dose-dependent improvement by treatment with MR13A9 at doses $\geq 0.5 \,\mu g/kg$. With respect to safety, the incidence of adverse drug reactions was 23.8% (5/21 subjects), 33.3% (7/21 subjects), 61.9% (13/21 subjects), 47.4% (9/19 subjects), and 82.6% (19/23 subjects) in the placebo, 0.25, 0.5, 1.0, and 1.5 µg/kg groups, respectively. Commonly reported adverse drug reactions (in ≥ 10% of subjects in any of the MR13A9 groups) included blood thyroid stimulating hormone decreased, dizziness, blood prolactin increased, nausea, feeling abnormal, and somnolence. The incidence of these adverse drug reactions was as follows: blood thyroid stimulating hormone decreased, 9.5% (2/21 subjects) in the 0.25 µg/kg group, 31.6% (6/19 subjects) in the 1.0 µg/kg group, and 30.4% (7/23 subjects) in the 1.5 μ g/kg group; dizziness, 4.8% (1/21 subjects) in the 0.25 μ g/kg group, 9.5% (2/21 subjects) in the $0.5 \mu g/kg$ group, 10.5% (2/19 subjects) in the $1.0 \mu g/kg$ group, and 17.4% (4/23 subjects) in the 1.5 µg/kg group; blood prolactin increased, 4.8% (1/21 subjects) in the $0.25 \mu g/kg$ group, 4.8% (1/21 subjects) in the $0.5 \mu g/kg$ group, 5.3% (1/19 subjects) in the $1.0 \,\mu g/kg$ group, and 17.4% (4/23 subjects) in the $1.5 \,\mu g/kg$ group; nausea, 4.8% (1/21 subjects) in the 0.25 μg/kg group and 17.4% (4/23 subjects) in the 1.5 μg/kg group; feeling abnormal, 4.8% (1/21 subjects) in the 0.5 µg/kg group and 17.4% (4/23 subjects) in the 1.5 µg/kg group; and somnolence, 4.8% (1/21 subjects) in the 0.25 µg/kg group, 4.8% (1/21 subjects) in the 0.5 µg/kg group, and 13.0% (3/23 subjects) in the 1.5 µg/kg group.

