7.5 Randomization and Blinding

7.5.1 Treatment Assignment

The person responsible for treatment assignment will prepare a treatment assignment table to assign subjects to MR13A9 0.25, 0.5, or 1.0 μ g/kg, or placebo at a ratio of 1:1:1:1.

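### The third of the five primary dose-response contrasts has five coefficients for four groups and sums to +1, so it cannot be run as written; (1, 1, -1, -1) is the likely intent

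*SAP*

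**What the plan says.** The primary analysis in SAP 10.1.1.1.1 is a repeated-measures model for change from baseline in mean NRS score. Dose-response is examined through contrasts at Week 8 (the primary variable) and at Week 2. The order of the coefficients is fixed by "Contrast patterns (placebo, 0.25, 0.5, 1.0" μg/kg), which gives four positions for the four groups randomised under protocol 7.5.1 ("or placebo at a ratio of 1:1:1:1"). Five patterns are listed, and the middle three read "2, 2, -1, -3), (1, 1, 1, -1, -1), (3, -1, -1, -1". The first pattern is (3, 1, -1, -3) and the last is (3, 1, -2, -2). Protocol 13.5.2.1.1 prints the same list.

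The SAP then requires that "P-values will be presented for each contrast pattern used to examine the dose-response relationship". In SAP 10.1.1.1.2, both multiple-imputation analyses use the contrasts again: "as with the primary analysis, contrasts will be used to determine dose-response relationships and estimate treatment effects". Nothing in either document explains or corrects the third pattern, and SAP section 2, which lists changes from the protocol, does not mention it.

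**The concern.** A contrast among four group means needs one coefficient per group, and the coefficients must sum to zero so that the expected value is zero when all groups respond alike. The third pattern fails on both counts. As printed, it defines no test.

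Someone must therefore repair it by choice, and the written plan does not say how. Dropping the last number to make the vector fit gives (1, 1, 1, -1), which sums to +2 and would reject merely because patients improve in every group. Other repairs are valid contrasts but test different dose-response shapes with very different power. Determining the dose-response relationship is the study objective, and SAP 6.5.3 cites the use of contrasts as its reason for not adjusting for multiple groups. The list should leave nothing to be settled after the data are seen.

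**Working it through.** **1. Count and sum of each printed pattern**

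| Pattern | Coefficients | Sum |
|---|---|---|
| (3, 1, -1, -3) | 4 | 0 |
| (2, 2, -1, -3) | 4 | 0 |
| (1, 1, 1, -1, -1) | 5 | +1 |
| (3, -1, -1, -1) | 4 | 0 |
| (3, 1, -2, -2) | 4 | 0 |

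**2. Which single deletion restores a contrast?** Removing any one of the three 1s gives (1, 1, -1, -1), sum 0. Removing either -1 gives (1, 1, 1, -1), sum +2. So (1, 1, -1, -1) is the only valid contrast one deletion away. The nearest other reading, (1, 1, 1, -3), needs one coefficient deleted and another changed.

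**3. What the truncated vector would test.** Suppose all four groups changed by -1.9, the placebo change that protocol 7.6.2 reports from the non-Japanese phase II study. Then (1, 1, 1, -1) has expected value 2 × (-1.9) = -3.8 instead of 0. With SD 2.5 and 60 per group, the standard error is 2.5 × √(4/60) = 0.645, so the statistic would centre near -5.9 with no treatment effect at all.

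**4. Inputs for power (protocol 7.6.2).** The test is set up "with a two-sided significance level of 5% and a sample size of 60 subjects per group". At Week 8 the difference from placebo "was assumed to be -0.6, -1.3, and -1.3, respectively, with a common standard deviation of 2.5". At Week 2 the assumed differences are -0.4, -0.8 and -0.8, with SD 1.9.

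For coefficients c and means μ (placebo = 0), the noncentrality is

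ncp = |Σcμ| / (SD × √(Σc²/60)), with df = 4 × (60 − 1) = 236,

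and power comes from the noncentral t distribution, two-sided 5%.

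**5. The plan's own figures first, for (3, 1, -2, -2), Σc² = 18**
- Week 8: Σcμ = -0.6 + 2.6 + 2.6 = 4.6; ncp = 4.6 / (2.5 × √(18/60)) = 3.359; power 91.7%, as stated.
- Week 2: Σcμ = -0.4 + 1.6 + 1.6 = 2.8; ncp = 2.8 / (1.9 × √(18/60)) = 2.691; power 76.4%, as stated.

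**6. The candidate repairs**

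| Vector | Σc² | Week 8: Σcμ, ncp, power | Week 2: Σcμ, ncp, power |
|---|---|---|---|
| (1, 1, -1, -1) | 4 | 2.0, 3.098, 87.0% | 1.2, 2.446, 68.3% |
| (1, 1, 1, -3) | 12 | 2.0, 1.789, 42.9% | 1.2, 1.412, 29.0% |

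**7. Overlap with the powered contrast (equal group sizes).** For (1, 1, -1, -1), the correlation with (3, 1, -2, -2) is (3 + 1 + 2 + 2) / √(18 × 4) = 8/8.485 = 0.94. For (1, 1, 1, -3) it is (3 + 1 − 2 + 6) / √(18 × 12) = 8/14.697 = 0.54.

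**8. Family-wise error at Week 8 with no effect.** In a simulation of 4,000,000 draws, the chance that at least one unadjusted contrast is significant is 10.1% for the four valid patterns and 10.8% with (1, 1, -1, -1) added. Nearly all of this comes from testing several contrasts without adjustment; the misprint contributes little.

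**The case against.** The strongest reply is that this is a recoverable misprint. The sample size rests on (3, 1, -2, -2), four contrasts are intact, a programmer cannot assign five numbers to four groups without noticing, and the obvious repair barely moves the family-wise error. All of that is true and limits the impact. It does not supply the missing definition: the plan asks for a p-value from a test that it does not specify, in its primary analysis.

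Second, both documents are certified translations from Japanese, so the operative plan may be correct. That stands as a possibility. The identical string in two documents makes a chance misreading less likely but does not exclude a shared error in the English.

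Third, the outside support for (1, 1, -1, -1) is only partial. Protocol 7.6.2 does assume equal effects at 0.5 and 1.0 μg/kg, but it gives 0.25 μg/kg about half the effect, a shape that (3, 1, -2, -2) already covers. Protocol 1.3.2.2 says "These results suggested a dose-dependent improvement by treatment with MR13A9 at doses" of 0.5 μg/kg and above, yet its figures rise gradually: 28.0, 32.8 and 41.2 mm at 0.5, 1.0 and 1.5 μg/kg, against 26.4 mm on placebo. That is not a flat step. This objection is fair. The case for (1, 1, -1, -1) rests on the deletion argument, which suffices for a likely reading but not for a certain one.

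Fourth, SAP 6.5.1 treats time points other than Week 8 as references, so the Week 2 gap carries less weight.

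**Conclusion.** The concern holds. In the English text of both documents, one of the five pre-specified dose-response contrasts is not a contrast and cannot be computed as printed. The gap affects one reported p-value at Week 8, one at Week 2, and their counterparts in the two multiple-imputation analyses.

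If the intent was a step at 0.5 μg/kg, restoring it changes little, since the test largely duplicates the powered contrast. If the intent was a top-dose-only shape, Week 8 power would be roughly half as large. The power figures assume the protocol's means and SDs, 60 evaluable subjects per group and a single-time-point comparison without covariates; that set-up reproduces the protocol's stated powers. The intended vector is inferred, because neither document states it. The correction should be made, but it does not call the design or the sample size into question.

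**What to change.** Compare the third pattern with the Japanese source of both documents and with the coefficients in the analysis program. Then, before unblinding, replace it in protocol 13.5.2.1.1 and SAP 10.1.1.1.1 with the intended four-coefficient, zero-sum vector, presumably (1, 1, -1, -1). State the dose-response shape it represents; for that vector it is no effect at 0.25 μg/kg and an equal effect at 0.5 and 1.0 μg/kg. If the Japanese text is right, correct only the translation.

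The cost is one check and one line in each document. No sample-size or power statement needs to change.
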